5.4 Sequencing pipeline

Robust next-generation sequencing strategies for the identification of neoantigens will be required for the successful clinical translation of personalized cancer vaccine strategies. As such, a major focus of our research studies has been the development of cost-effective and accurate next-generation sequencing strategies to identify neoantigens and validate the expression of these antigens at the mRNA level.

The first step in the sequencing pipeline is exome sequencing of pancreatic cancer and normal DNA. Exome fragments are captured using Nimblegen's "VCRome" exome capture reagent. Background DNA is washed away while the bound exome DNA is eluted and sequenced. Separate libraries are made from the pancreatic cancer and normal DNA and processed independently. Exome sequencing is performed using the Illumina platform.

Exome sequences from pancreatic cancer and normal DNA are compared separately to the human reference sequence and then to one another to identify somatic variation. VarScan 2 software is used to detect misaligned sequences and identify structural variants in the pancreatic cancer DNA.

The second step in the sequencing pipeline is cDNA-capture sequencing. To validate the results of the exome sequencing, and confirm expression of the somatic mutations in the pancreatic cancer, cDNA-capture sequencing of the pancreatic cancer RNA will be performed. cDNA-capture sequencing is very similar to RNA sequencing, but cDNA is captured prior to sequencing to enrich for mRNA. cDNA-capture sequencing is a sensitive and accurate methodology to detect expression of somatic mutations at the mRNA level in pancreatic cancer. cDNA-capture sequencing is performed using the Illumina platform.

Additional details are included in the "Sequencing Pipeline" section of IND 16509.

5.5 Epitope prediction algorithm

We have developed and optimized an epitope prediction algorithm for the identification and prioritization of neoantigens. This optimized epitope prediction algorithm is described below and in the Gubin 2014 manuscript [25]. We have established this algorithm in collaboration with [name], an internationally-known expert in tumor immunology [24, 34-41]. [name] was one of the first to use next generation sequencing technologies to identify neoantigens, demonstrating that these antigens are important tumor rejection antigens [24]. [name] and [name] have now optimized the epitope prediction algorithm and have demonstrated that cancer vaccines targeting neoantigens are associated with antitumor immunity [25].

The goal of the optimized epitope prediction algorithm is to identify and prioritize up to 20 neoantigens. The algorithm uses a combination of binding algorithms, processing algorithms and *in vitro* binding assays.

Mutations that are expressed in the pancreatic cancer will be identified using the sequencing pipeline outlined in the document titled "Sequencing Pipeline." The predicted amino acid sequences corresponding to the expressed mutations will be pipelined through multiple class I and class II MHC epitope-binding algorithms provided by the Immune Epitope Database and Analysis Resource (<http://www.immuneepitope.org>) including but not limited to (i) Stabilized Matrix Method (SMM) [42], (ii) Artificial Neural Network (ANN) [43], and (iii) NetMHCpan [44].

A prioritized list of binding epitopes (i.e. $IC_{50} < 500$ nM) will be generated after calculating the median binding affinity value for each mutant sequence (affinity value expressed as $1/IC_{50} \times 100$).

Filters will be applied to the list to (a) eliminate epitopes that are not processed efficiently by the immunoproteasome based on the NetChop algorithm [45] (peptides with a NetChop score ≥ 0.6 will be prioritized), (b) deprioritize epitopes from hypothetical proteins or that form a weaker predicted binding epitope than that expressed by the corresponding wild type sequence, (c) prioritize mutant epitopes that have the highest difference in predicted binding affinity compared to their wild type counterpart, and (d) incorporate expression profiles of wild type genes that correspond to the mutant antigen candidates in normal vs tumor cells.

Additional details are included in the "Epitope Prediction Algorithm" section of IND 16509.

6 TREATMENT PLAN

6.1 Peptide Vaccine administration

All subjects will be treated as outpatients in the Siteman Cancer Center/Sidney Kimmel Comprehensive Cancer Center.

Patients with pathologically verified R0/R1 surgical resection and no evidence of recurrent and/or metastatic disease will be identified for tissue procurement and sequencing. Patients will initiate gemcitabine/capecitabine or comparable adjuvant chemotherapy no more than 16 weeks following resection. Adjuvant chemotherapy will be administered for a total of six cycles as per the NCCN recommendations for adjuvant chemotherapy following surgical resection. Additional chemoradiation, dose modifications, reductions, and supportive care will be performed at the discretion of the treating medical oncologist. After completion of adjuvant chemotherapy, patients will undergo repeat imaging by CT scan and/or MRI to evaluate for disease recurrence. Patients with no evidence of disease as determined by a board certified radiologist and without rising levels of tumor markers will be eligible for vaccination. If vaccine production is unable to be completed for a particular patient, that patient will discontinue participation in this study and will be replaced.

The schedule for vaccination will be Days 1, 4, 8, 15, and 22 (delays of up to 96 hours are allowed for each dose based on the AEs experienced). Additional vaccinations will be given on Days 50 and 78 (+/- 2 weeks). The first vaccine dose may be administered following confirmation of disease-free status and within 90 days following date of repeat imaging. All study injections will be given subcutaneously and co-administered with poly-ICLC by a trained healthcare provider. At each vaccination time point, patients will receive up to four injections of the neoantigen peptide vaccine + adjuvant. The peptides and poly-ICLC will be mixed prior to injection. Standard aseptic technique and precautions will be utilized in site preparation, vaccine administration, and medical waste disposal to ensure maximal safety of subjects and study personnel. Please refer to Section 5.10 for Vaccine preparation instructions.

At the discretion of the treating physician, patients may be pre-medicated with lorazepam 1mg PO at least 30 minutes but no greater than 60 minutes prior to the first injection. Patients may also receive a second dose of lorazepam (1 mg PO) 10 minutes prior to injection. Patients may also receive acetaminophen 650mg PO at least 30 minutes but no greater than 60 minutes prior to the first injection.

Following study injections, subjects will be observed for a minimum of 30 minutes. Vital signs (temperature, blood pressure, pulse and respiratory rate) will be taken at 30-45 minutes post-immunization. The injection sites will be inspected for evidence of local reaction.

On each injection day (prior to injection), study subjects will be evaluated by clinical exam and laboratory tests. Post-vaccination follow-up visits are at 4 weeks following last injection (\pm 7 days) and 1 year following last injection (\pm 14 days). Additional follow-up visits or telephone contact will be scheduled annually thereafter if the patient is alive and available for follow-up.

At intervals throughout the study (both before and after vaccination) subjects will have blood drawn for immunologic assays. Any cells, serum or plasma not used will be stored for future immunological assays.

Please see **Section 8 Study Calendar** for details on study visit procedures and monitoring.

6.2 Concomitant Medication Guidelines

Patients may receive other vaccinations while on study, including influenza and pneumococcal.

Patients will be treated for toxicities at the discretion of the physician. Growth factor support with either filgrastim or pegfilgrastim is at the discretion of the investigator.

There are no prohibited medications.

6.3 Definitions of Evaluability

All enrolling patients are evaluable for the primary objective of feasibility, even patients whose tumor/normal exome sequencing is not completed or who are unable to have vaccine manufactured or administered.

A patient must have received at least one injection of vaccine in order to be evaluable for the primary objective of safety and the secondary objective (prevalence of antigen-specific T cells in peripheral blood).

6.4 Duration of therapy

In the absence of treatment delays due to adverse events, treatment may continue for 7 doses of neoantigen peptide pancreatic cancer vaccines. Under certain circumstances, a subject will be terminated from participating in further injections. Subjects who are discontinued from additional study injections will continue to be followed according to the schedule of safety and immunogenicity evaluations. Please see **Section 10 Removal of Patients from Protocol Therapy** for additional details.

6.5 Duration of follow up

Patients will be examined at 4 and 52 weeks following the final vaccination. Additional follow-up visits or telephone contact will be scheduled every year thereafter if the patient is alive and available for follow-up. Patients removed from study for unacceptable adverse events will be followed until resolution or stabilization of the adverse event.

7 POTENTIAL TOXICITY AND DOSE MODIFICATIONS

7.1 Potential toxicity

7.1.1 Potential toxicity related to the neoantigen peptide vaccine

This is the one of the first times that mutant tumor-specific antigens identified by next generation sequencing have been targeted for immune therapy in humans, and one of the first times that personalized synthetic long peptide vaccines have been administered to humans. However, clinical trials of similar investigational peptide vaccines suggest that these vaccines will be very safe. We expect that most of the toxicity to be limited to local grade 1 or 2 reactions at the site of vaccination.

Please note that the risks detailed below are based on the risks of injections, the risks of vaccines in general, and the results of previous studies with investigational DNA vaccines.

Risks associated with subcutaneous injections include acute bleeding and/or bruising. Although highly unlikely, intradermal injection can result in injection site infection. As with any immunization, discomfort or redness at the injection site in the days following vaccine administration may be expected.

Subjects may exhibit general signs and symptoms associated with administration of a vaccine injection, including fever, chills, rash, aches and pains, nausea, headache, dizziness and fatigue. These side effects will be monitored, but are generally short term and do not require treatment.

7.2 Toxicity monitoring and management

Toxicity will be characterized according to the National Cancer Institute Common Terminology Criteria for Adverse Events version 5.0 (CTCAE). Subjects who are immunized with the peptide vaccine will be evaluated at the time of each vaccination on days 1, 4, 8, 15, 22, 50 and 78. Adverse events will be reported to the Quality Assurance and Safety Monitoring Committee of the Siteman Cancer Center/Sidney Kimmel Comprehensive Cancer Center, the Institutional Review Board, the Institutional Biosafety Committee, the Office of Biotechnology Activities and the Food and Drug Administration as detailed in **Section 11 Adverse Event Reporting**.

Significant local inflammation will be treated with cold packs and oral analgesics as indicated. Skin ulceration at the vaccine site will be treated with local wound care and antibiotics as indicated. Development of signs and/or symptoms of autoimmune involvement will be initially treated conservatively with analgesics. More aggressive intervention (systemic corticosteroids) will be used as necessary and will result in termination of future vaccine inoculation.

7.3 Dose modifications

No dose modifications are planned. If a subject develops an adverse event that is classified as possibly, probably, or definitely associated with protocol therapy, this may result in removal of the subject from protocol therapy as outlined in **Section 10 Removal of Subjects from Protocol Therapy**. Protocol Stopping Criteria are outlined in **Section 12 Data and Safety Monitoring**.

8 STUDY CALENDAR

The window for Step 0 screening procedures is up to 28 days prior to enrollment. Enrollment must occur within 28 days of the patient starting on adjuvant therapy. The window for Step 1 screening procedures is 14 days prior to first vaccine dose.

	Step 0 Screening	Step 1 Screening	Day 1	Day 4 ^f	Day8 ^f	Day15 ^f	Day 22 ^f	Day 50 (+/-2wk)	Day 78 (+/-2wk)	EOT	F/U ^h
Neoantigen peptide vaccine ^{a,i}			X	X	X	X	X	X	X		
Informed consent	X										
Demographics	X										
Medical history	X										
Physical exam	X	X	X	X	X	X	X	X	X	X	X
Concurrent Meds	X ----- X										
Vital signs	X	X	X	X	X	X	X	X	X		X
Height	X										
Weight	X	X	X	X	X	X	X	X	X		X
Performance Status	X	X	X	X	X	X	X	X	X		
CBC w/diff, plts	X	X	X				X	X	X		
CMP ^b	X	X	X				X	X	X		
INR, PTT	X	X									
EKG	X	X									
Radiologic evaluation	Radiologic measurements will be performed as clinically indicated. Documentation of tumor recurrence or metastatic disease must be provided for patients removed from study for progressive disease.										
Adverse event evaluation			X ^g	X ^g	X ^g	X ^g	X ^g	X ^g	X ^g	X	X
B-HCG	X ^e	X ^e	X ^e	X ^e	X ^e	X ^e	X ^e	X ^e	X ^e		
Immune monitoring ^c	X		X				X	X	X		X ^j
Pathology Review ^d	X										
Eligibility Confirmation	X	X									

a: Personalized synthetic long peptide pancreatic cancer vaccine

b: Albumin, alkaline phosphatase, total bilirubin, bicarbonate, BUN, calcium, chloride, creatinine, glucose, LDH, phosphorus, potassium, total protein, SGOT [AST], SGPT [ALT], sodium.

c: Immune monitoring labs to consist of seven 10mL green top heparin tubes for isolation of PBMCs. During adjuvant therapy, the mid and end of chemo draws are optional. Generally, these should occur at a clinic visit associated with the restaging scan, as well as at each follow up visit. This will yield approximately 50-200 x10⁶ PBMCs per collection.

d: Pathology review to confirm diagnosis of adenocarcinoma and evaluate tumor cellularity.

e: Serum or urine pregnancy test (women of childbearing potential).

f: +/- 1 days with at least 24 hours between vaccinations

g: Adverse event evaluation on day of vaccine

h: ± 28 days; follow-up or telephone contact at 4 weeks and 1 year after last injection and annually thereafter if the patient is alive and available for follow-up. F/U visits may be done at the participant's local MD office.

i: patients may discontinue participation if vaccine production is unable to be completed

j: optional based on patient availability

9 CRITERIA FOR RESPONSE

9.1 Primary objective: safety

Assessment of synthetic long peptide safety will include both clinical observation and laboratory evaluation. Safety will be closely monitored after injection with eight or more clinical and laboratory assessments in the first 24 weeks of the trial. The following parameters will be assessed following vaccination:

- (1) Local signs and symptoms
- (2) Systemic signs and symptoms
- (3) Laboratory evaluations, including blood counts and serum chemistries
- (4) Adverse, and serious adverse events

Toxicity will be graded according to the National Cancer Institute Common Terminology Criteria for Adverse Events v5.0.

9.2 Secondary objectives: evaluation of the immune response

9.2.1 Introduction to immune monitoring

The secondary endpoint is to evaluate the immunogenicity of the neoantigen peptide vaccine. Immunogenicity will be measured by ELISPOT analysis, a surrogate for CD4 and CD8 T cell function, and multiparametric flow cytometry. In both assays the quantity and quality of antigen-specific T cells is determined; the ELISPOT analysis is based on measuring the frequencies of IFN- γ producing T cells in response to polyepitope antigen, whereas the multiparametric flow cytometry assesses phenotypic as well as functional characteristics of epitope-specific T cells. In the proposed study, blood samples will be collected at multiple time points (n=8) and PBMC isolated and cryopreserved. Upon completion of the vaccination protocol, all samples will be analyzed simultaneously in order to minimize assay-to-assay variation.

9.2.2 Sample collection and processing

During Step 0 enrollment, tumor samples will be reviewed by a pathologist with expertise in pancreatic cancer who will review the operative specimen slides to verify tumor cellularity and quantity sufficient for proceeding. Once tissue viability is confirmed, specimens from outside Washington University will be shipped to the [name] lab at the following address: [name] Lab, [name]. The corresponding FFPE blocks will be punched with a disposable 1mm biopsy punch. 6-8 full thickness punches will be taken from areas of high tumor cellularity and divided evenly into two DNA LoBind Eppendorf tubes (one tube for DNA and one for RNA). To identify somatic mutations, DNA and RNA will be extracted from the FFPE preserved tissue by the Center for Human Immunology and Immunotherapy Programs (CHiiPS) core. All tissue selected for sequencing will be processed into a single-cell suspension by mechanical and enzymatic digestion, and used to extract nucleic acids. Tumor DNA + RNA will then undergo tumor exome and tumor cDNA-capture sequencing, respectively at the Genome Institute. Normal genomic DNA will be isolated from PBMCs by the CHiiPS core or [name] laboratory personnel for normal exome sequencing at The Genome Institute.

Patients will undergo their first blood draw during Step 0 screening to establish a baseline for immune monitoring and for creation of the vaccine. This first blood draw will be shipped ambient same day of draw to the [name] lab at the following address: [name] Lab, [name]. Additional optional pre-vaccine blood samples will be obtained midway through chemotherapy and at the end of chemotherapy. Immune monitoring labs will be draw prior to vaccination on Days 1, 22, 50, and 78. Post- vaccine immune monitoring labs will be drawn at the first two follow-up time points (4 weeks after last injection and 1 year after last injection). Seven collection tubes (BD Vacutainer® sodium heparin (green top), REF 367874, 10 mL each for a total of approximately 70 mL) are filled by venipuncture at each time point. Blood samples will be transported to [name]/JHU equivalent laboratory ([name]) within one hour of collection. PBMC will be obtained by Ficoll-Hypaque gradient centrifugation and cryopreserved in 10%

DMSO according to standard procedures. Blood will be batch shipped to the [name] lab at the address listed above. Exome sequencing of PBMC will be performed to obtain germline sequences.

9.2.3 ELISPOT Analysis

ELISPOT analysis, will be performed as previously described [46-50]. PBMC from subjects in the phase 1b clinical trial will be tested for secretion of IFN- γ by ELISPOT assay. PBMC will be plated at various concentrations starting at 300,000 cells per well, in triplicate, following the protocol previously described by [name] and colleagues. PBMC will be co-cultured with the mutant and mesothelin peptides encoded by the polyepitope construct. As negative controls, PBMC will be incubated in medium alone or stimulated with matching wild type peptides. As a positive control we will include a mix of viral peptides, CEF, containing immunodominant epitopes for multiple common HLA alleles from influenza virus, cytomegalovirus, and Epstein-Barr virus. After 24-48 hours, the plates will be developed and the spots counted in an ImmunoSpot Series I analyzer (Cellular Technology).

9.2.4 Multi-parametric flow cytometry

Patient-derived PBMC will be used for functional assays to characterize immunity to personalized pancreatic cancer DNA vaccines. Polyfunctional CD8 T cell responses will be determined after stimulation of cultured PBMC with polyepitope pulsed autologous PBMC using multi-parameter flow cytometry. Fluorescently labeled MHC class I tetramers expressing vaccine-encoded peptides will be used to gate on peptide-specific T cells. The choice of tetramers to be used in these analyses will be dictated by the neoantigens and mesothelin antigens used for a given patient's personalized vaccine, and the patient's HLA phenotype. We will also simultaneously stain tetramer-positive and tetramer-negative CD8 T cells for a variety of well-accepted markers that report the functional status of antigen specific CD8 T cells. These include the cell surface markers PD-1, CTLA-4, LAG-3, and TIM-3 (markers of T cell inactivation), the proliferation marker Ki-67, and the cellular activation markers ICOS, granzyme B, TNF- α and IFN- γ . We have already validated all of our staining reagents and demonstrated that specific combinations of mAb labeled with different fluorescent tags can be used together allowing for multi-color analysis in a single run. Analyses will be performed using either a BD Fortessa (6-color analysis) or BD LSR II cytometers (11-color analysis). A positive effect of immunotherapy is expected to show increased numbers of tetramer-positive cells that also display decreased expression of PD-1, CTLA-4, LAG3, and TIM3, and increased staining for Ki-67, ICOS, granzyme B, TNF- β and IFN- γ .

PBMC aliquots (2×10^6 cells/mL) will be stimulated with individual peptides encoded by the polyepitope vaccine and cultured in the presence of IL-2 (50U/mL). Ten days after activation, cells will be harvested, washed and restimulated with irradiated (10,000 rads) peptide-pulsed autologous PBMC for 16h (in the presence of Brefeldin A) and stained with antibodies for the various markers listed above. Cells will be analyzed by the Immune Monitoring Core, also known as the Center for Human Immunology and Immunotherapy Programs (CHiIPs), headed by [name]. Cultured cells stimulated with unpulsed PBMC will be used as negative control, and cells stimulated with CEF-pulsed PBMC will be used as positive controls using an appropriate tetramer. One advantage of using 10 day activated/antigen-driven PBMC to measure polyfunctional responses is the expected relative high frequency of polyepitope-specific T cells providing a larger sample size for statistically significant data analysis.

10 REMOVAL OF SUBJECTS FROM PROTOCOL THERAPY

10.1 Removal of subjects from protocol therapy

Subjects may be removed from protocol therapy if any one or more of the following events occur:

- (1) Development of recurrent or metastatic disease prior to the initial vaccination will result in stopping vaccine development at its current stage;
- (2) Development of recurrent or metastatic disease during the vaccination period will result in stopping further vaccinations. Due to the high recurrence rate associated with pancreas cancer, it is expected that some percentage of patients will recur during the period of vaccine production and administration. Due to the poor response to traditional chemotherapeutics, patients who recur or develop metastatic disease may still benefit from vaccine administration, vaccine administration in combination with chemotherapy, and/or checkpoint blockade. The decision to continue or discontinue vaccine administration will be left to the treating physician.
- (3) Intercurrent illness that prevents further administration of protocol therapy;
- (4) Pregnancy;
- (5) Type 1 hypersensitivity reaction associated with protocol therapy;
- (6) Grade 2 systemic or injection site adverse event classified as possibly, probably, or definitely associated with protocol therapy that does not resolve to at least grade 1 prior to the next scheduled treatment excluding priming vaccine on Days 1, 4, 8, and 15, where dose delays are permitted per Section 6);
- (7) Grade 3 or 4 systemic or injection site adverse event classified as possibly, probably, or definitely associated with protocol therapy;
- (8) Any significant autoimmune disease or phenomena presumed to be related to protocol therapy;
- (9) Unable to complete vaccine production;
- (10) Subject refusal to continue protocol therapy and/or observations;
- (11) Significant protocol violation or noncompliance, either on the part of the subject or investigator(s);
- (12) The principal investigator or study sponsor believes it is in the subject's best interest to discontinue participation in the study;
- (13) Administrative reasons, e.g., study termination by the principal investigator, Siteman Cancer Center/Sidney Kimmel Comprehensive Cancer Center, HRPO, FDA, or other group.

Please note that even if a subject is removed from protocol therapy, they will continue to be followed for adverse events for 30 days after last injection, and thereafter only report treatment related SAEs or AEs.

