1.2 Secondary objective

The secondary objective, and primary scientific endpoint, is to assess the prevalence of antigen-specific T cells in the peripheral blood of patients pre- and post-vaccination as measured by flow cytometry and ELISPOT.

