11 REGULATORY AND REPORTING REQUIREMENTS

The entities providing oversight of safety and compliance with the protocol require reporting as outlined below. Please refer to Section 20.4 for definitions and Section 20.6 for a grid of reporting timelines.

Adverse events will be tracked from start of treatment through 30 days following the last day of study treatment. All adverse events must be recorded on the toxicity tracking case report form (CRF) with the exception of:

- Baseline adverse events, which shall be recorded on the medical history form

Refer to the data submission schedule in Section 14 for instructions on the collection of AEs in the EDC.

Reporting requirements for Washington University study team may be found in Section 11.1. Reporting requirements for secondary site study teams participating in Washington University-coordinated research may be found in Section 11.2

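### A T-cell response first seen on checkpoint blockade or other therapy started after recurrence would enter the section 13.2.2 response rate unmarked

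*Combined protocol and SAP*

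**What the plan says.** Section 10.1 opens with "Subjects may be removed from protocol therapy if any one or more of the following events occur". Item (2) then sets the default at recurrence: "Development of recurrent or metastatic disease during the vaccination period will result in stopping further vaccinations". The same item foresees that this will happen ("it is expected that some percentage of patients will recur during the period of vaccine production and administration"), says that such patients "may still benefit from vaccine administration, vaccine administration in combination with chemotherapy, and/or checkpoint blockade", and ends with "The decision to continue or discontinue vaccine administration will be left to the treating physician". Read with the permissive opening, this is a default stop with a physician override.

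Five other places decide what happens to these patients' immune samples:

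- Section 6.2 prohibits no medication.
- Section 6.3 makes a patient evaluable for the immune objective after one injection.
- Section 6.4 keeps patients who stop injections on the immunogenicity schedule.
- Section 9.2.2 sets immune draws before vaccination on Days 1, 22, 50 and 78, then 4 weeks and 1 year after the last injection. Footnote j of the Study Calendar makes the follow-up draws optional.
- Section 13.2.2 defines a positive response as a post-vaccination T-cell number more than 2 SD above the pre-vaccination mean. It reports a binomial rate with a 95% confidence interval at each time point.

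Section 1.2 gives this endpoint unusual weight for a secondary one: "The secondary objective, and primary scientific endpoint, is to assess the prevalence of antigen-specific T cells".

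**The concern.** The immune result is meant to describe the immunogenicity of the vaccine. The 13.2.2 rule looks only at the T-cell value and its timing relative to vaccination. It has no condition, flag or second display for samples drawn after another anticancer drug has been started. The only data cut-off stated is withdrawal of consent (10.2).

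The protocol's own preclinical work makes this kind of mixing plausible. In section 5.3.2, T-cell lines from mice that had rejected their tumour after anti-PD-1 therapy recognised the prioritised neoantigens. T cells specific for those neoantigens also accumulated in tumours of anti-PD-1-treated mice. No vaccine is mentioned in those two experiments. A patient whose count first crosses the threshold on checkpoint blockade could therefore be a drug responder reported as a vaccine responder. Responder status also feeds the exploratory survival comparison in 13.2.3, which has no rule for responses first seen after recurrence.

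**Working it through.** **1. The plan's own figure.** Section 13.1.3 states 80% power for a paired t-test with n = 15, an increase of 0.68 SD and one-sided alpha 0.05. With 14 degrees of freedom and noncentrality 0.68 × √15 = 2.63, exact power is 80.5%. The figure reproduces, and nothing below changes it.

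**2. Which samples are exposed.** Step 1 (3.3) requires clear imaging after chemotherapy and CA 19-9 below 92.5 u/mL. The first dose falls within 90 days of that imaging (6.1). Later imaging is only as clinically indicated (section 8). Five immune samples follow Day 1; the days below assume all doses are on schedule.

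| Sample | Days since first dose | Exposure to new therapy |
|---|---|---|
| Day 22 | 22 − 1 = 21 | Unlikely: recurrence must be found and treatment begun within three weeks |
| Day 50 | 50 − 1 = 49 | Possible |
| Day 78 | 78 − 1 = 77 | More exposed |
| 4 weeks after last dose (optional) | 78 + 28 = Day 106, so 105 | More exposed |
| 1 year after last dose (optional) | 78 + 364 = Day 442, so 441 | Most exposed |

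The mixing does not depend on the override. A patient who stops vaccine and starts other therapy is still sampled under 6.4.

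**3. Shift per patient.** One patient who is positive at a time point only because of other therapy raises that rate by 1/n, where n is the number sampled:

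- n = 15: 1/15 = 6.7 points
- n = 12 (assumed): 1/12 = 8.3 points
- n = 10 (assumed): 1/10 = 10.0 points
- n = 8 (assumed): 1/8 = 12.5 points

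**4. Illustration, with assumed counts.** Suppose 7 of 15 patients respond to vaccine at a late time point: 46.7% (Clopper-Pearson 95% CI 21.3 to 73.4). Suppose three others are positive only because of new therapy. The rule in 13.2.2 then reports 10/15 = 66.7% (38.4 to 88.2). If the three samples are left out, the rate is 7/12 = 58.3%. The restricted rate is also above 46.7%, because it drops three patients who would otherwise have counted as negative. Neither rate is sufficient alone.

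**5. Would existing forms date the new therapy?** Under section 14 the Concomitant Medications Form runs through Week 25, which is 25 × 7 = Day 175 if counted from Day 1 (assumed). The latest 4-week sample depends on how the windows are anchored, which the protocol does not state:

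- All windows anchored to Day 1: 78 + 14 + 28 + 28 = Day 148, using the 28-day calendar window. With the 7-day window in 6.1 it is 78 + 14 + 28 + 7 = Day 127.
- Delays carried forward: four early doses each 4 days late, the Day 50 and Day 78 windows added, and the calendar window: 78 + 16 + 14 + 14 + 28 + 28 = Day 178.

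The form therefore ends well before the 1-year sample and possibly before a delayed 4-week sample.

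**The case against.** The strongest reply is that 13.2.2 labels values as positive and does not attribute each one to the vaccine. Section 13.2 calls the analysis descriptive, no decision threshold rests on the response rate, and using every post-vaccination sample regardless of later therapy is a legitimate choice in a small uncontrolled trial. That stands, and it is why the all-sample rate should stay. It does not explain why the reader should be unable to see which positives arose on another drug.

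Much of the raw information is also collected: concomitant medications, progression dates and vaccine administration. With 15 patients, a listing could show the issue. This too stands in part, but no such display is planned and the medication form stops early. The wild-type peptide control in the ELISPOT assay (9.2.3) helps to show mutation specificity. It cannot tell a vaccine-driven response from one driven by checkpoint blockade.

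A reader might infer that continuation after recurrence is unsupervised. The documents do not support that. Section 10.1(12) lets the principal investigator or sponsor discontinue a patient, 12.1 provides regular independent review of treatment and toxicity, and the 12.2 halting rules and DSMB review still apply.

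A reader might also infer that the safety results are badly contaminated. The exposure is limited. Section 11 states "Adverse events will be tracked from start of treatment through 30 days following the last day of study treatment", and for removed patients 10.1 says "they will continue to be followed for adverse events for 30 days after last injection, and thereafter only report treatment related SAEs or AEs". Full collection thus ends at 78 + 30 = Day 108 on schedule, or 78 + 14 + 30 = Day 122 if the last dose is two weeks late against Day 1. The listing in 13.2.1 already gives onset and relationship to treatment.

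**Conclusion.** The point holds as a gap in how the immune response rate is reported. As written, 13.2.2 mixes vaccine responses with any that first appear on later anticancer therapy, in what the protocol calls its main scientific endpoint.

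The size per patient is 6.7 points at a time point where all 15 are sampled, and more where fewer attend. The total cannot be given, because the documents state no recurrence rate, continuation rate or rate of checkpoint blockade use. The net direction is not fixed either: chemotherapy could lower counts.

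Three stronger readings are tempting and should be resisted:

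- That the response rate will be inflated by a known amount. Without the missing rates, only the shift per patient can be stated.
- That all five later samples are equally at risk. Rates are reported per time point, so any time point without samples on new therapy is unaffected, and Day 22 is unlikely to be affected.
- That the sample size or power is wrong. The stated 80% reproduces.

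**What to change.** Record the start date of any new anticancer therapy on the Progression Form and the Follow Up Form. In 13.2.2, flag immune samples taken after that date. Report each time-point response rate two ways, each with its denominator: all samples, and only samples taken before new therapy.

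The cost is one date on existing forms, one flag and one more column in the response table. No patient or sample is dropped from the main result. The downside is that the restricted rate has fewer late samples and favours patients without recurrence, so it supplements the all-sample rate and does not replace it.

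Two further changes are optional clarifications and not part of this fix: rewording 10.1(2) so that the default stop and the physician override are explicit, and flagging adverse events with onset after new therapy. The rewording alone would not solve the problem, because patients who stop vaccine and start other therapy are still sampled.
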